#### 4.2.1.2 Description of recruitment contacts

The recruiter will walk up to potential participants and introduce the project according to a recruitment script. We will then perform the first stage of eligibility assessment. MSM and MSW who are not eligible for reasons other

than insertive partner status will be thanked for their time, but no identifying information will be collected. MSM who are not eligible because they are not the insertive partner may be asked to give a contact card to their partner, if applicable. Those eligible will be asked to provide a first name, first, middle (if applicable) and last initial, email address, and phone number(s) if they are willing to be contacted for further screening and potentially scheduled for an informed consent and baseline visit. Responses to screening questions will not be saved in the study database, with all eligibility criteria to be re-assessed and entered into the study database at the baseline visit (the third screening stage). The following script is one example of the type of communication that will be used to initiate contact in the field:

"Hi, my name is [name] and I am working with Emory University on a men's health study. Can I ask you a few questions to see if you are eligible to participate?"

### 4.2.2 Secondary recruitment methods

If primary recruitment methods do not identify a sufficient number of either MSM or MSW, we will incorporate secondary recruitment methods, which may include (1) flyers and paid advertisements, (2) recruitment from previous studies, (3) recruitment through female partners or receptive MSM, and (4) recruitment through referrals

# 4.2.2.1 Flyers and paid advertisements

Based on recruitment progress, and counts of MSM and MSW recruited, we may supplement primary recruitment using flyers and paid advertisements targeting the study population of interest. We may post flyers advertising the study in venues that men frequent, such as community and clinical spaces, colleges and universities (e.g., cafes, clubs, bars/restaurants, gyms, HIV/STI testing facilities, doctors' offices, and sex shops). We may also create paid advertisements in popular social networking sites including facebook.com, twitter.com, other gay-friendly sites like scruff.com, and local news and culture sites like ctatl.com. Example advertisements are uploaded to eIRB.

#### 4.2.2.2 Recruitment from previous studies

We may recruit participants, who have consented to be contacted, from previous research projects conducted by our team in Atlanta (NIH study number: R01MH085600, R43HD078154, R01HD067111).

#### 4.2.2.3 Recruitment through partners

We may also perform venue-based or online recruitment through female partners of MSW and through receptive partners of MSM. MSM who are ineligible because they are receptive will be asked if they have a partner. If they do have a partner, they will be given a study contact card in case their partner would like to participate. Individuals who are ineligible through online recruitment may be asked to share the survey link with their male partner. We

9

may also have recruiters approach women and recruit their male partners through a series of questions.

# 4.2.2.4 Recruitment through referrals

Participants may be asked to provide a referral code to up to three peers. Peers who receive the code and visit the link will be given the opportunity to take an online eligibility screener and consent to be screened on the phone. Study staff will contact eligible and electronically consented individuals and complete the second stage of eligibility screening on the phone. Those eligible will be scheduled for a study visit.

# **4.3 Participant Retention**

Once a participant enrolls in the study, study staff will seek to retain the participant throughout the follow-up period in order to minimize possible bias associated with loss-to-follow-up. Study staff will be responsible for developing and implementing standard operating procedures to target this goal. Components of such procedures include:

- An explanation of the study and procedural requirements during the informed consent process and re-emphasis at each study visit.
- Collection of detailed contact information at the study baseline enrollment visit, and active review and updating of this information at each subsequent visit.
- Use of daily reminder mechanisms, such as SMS or email reminders, to complete coital log entries for each study condom use.
- Study staff follow-up after unanswered daily reminders.
- Use of SMS, telephone, or email reminder mechanisms prior to scheduled visits.
- Immediate follow-up on missed visits, with rapid rescheduling.
- Monthly attempts to reengage participants who have been unresponsive to scheduling attempts through the duration of the study.
- To reduce the burden of study visit attendance on participants who do not own a vehicle, we will make available prepaid single-ride MARTA cards or prepaid fare for a car service for transit to study visits.

#### 4.4 Participant Withdrawal

Participants may voluntarily withdraw from the study for any reason at any time. The study investigators also may withdraw participants from the study in order to protect participant or staff safety. Study staff will record the reasons for all withdrawals or holds from the study on a Study Stop Form in the participants' study records. Study stoppage may occur for the following reasons:

- Participants who self-report symptoms of STIs (described in more detail in section 7.1.2.2) will be referred to AID Atlanta for testing, but will be study stopped and will not attend follow-up visits.
- Participants who: (a) report that their current partner(s) is HIV-positive; (b) that they have had sex with someone in the past 30 days who is HIV-positive and plan to have sex with that partner again; or (c) add a new partner in the coital log who is HIV-positive

- during the study, will be study stopped and given information on pre-exposure prophylaxis (PrEP).
- Participants also may be withdrawn if the study is terminated prior to its planned end date.

Participants may be temporarily held from the study for the following reasons:

- Participants who have had unprotected anal sex with a man OR injected a substance not prescribed to them in the past 30 days AND self-report symptoms of acute HIV, such as fever over 100°F, at baseline or follow-up visits will be paused until a viral load test is performed. Participants will be study stopped if they have a detectable viral load; participants can resume study visits if their viral load is undetectable.
- Participants with a preliminary positive rapid HIV test at baseline will be paused until results of a confirmatory test are received. Participants will be study stopped if they are confirmed to be HIV positive; confirmed HIV negative participants will be asked to return to complete their baseline visit.
- Participants experiencing discomfort or issues related to the study condoms or lubricant will be paused until the study physician can assess the severity of issues. Participants will be study stopped if the physician determines it is in the participant's best interest to discontinue participation in the study.

### 5. STUDY PRODUCT

### 5.0 TheyFit Condom

TheyFit, LLC manufactures 56 condom sizes based on combinations of length (approximately 10 mm increments) and circumference (approximately 2 mm increments). To determine appropriate condom size, TheyFit, LLC developed a trademarked fitting tool. This tool is a paper template graduated with non-sequential numbering and lettering for maximum privacy. The FDA has accepted the sizing device as an instrument to determine fitted condom size. All references to "TheyFit" will be removed from the fitting tool and from all other study components. The study will use the full range of the 56 TheyFit, condom sizes cleared by the FDA. TheyFit condoms will be manufactured by Karex.

#### 5.1 Thin Condom

Thin condoms, as defined in section 1.1, were selected as an additional study condom because they are widely sold condoms in the United States and because of the general perception that are more pleasurable to use than standard condoms. Thin condoms will be manufactured by Karex.

### 5.2 Standard Condom

Standard condoms, as defined in section 1.1, were selected as the control because they are the most widely used condoms internationally due to their use by programs distributing condoms, such as USAID ([name], BS, email communication, June 23, 2015). Standard condoms will be manufactured by Karex.

#### 5.3 Lubricant

Study staff will provide participants with two packets per condom of 10ml commercially available condom-compatible water-based lubricants. Participants will be instructed not to use any other lubricants when using study condoms. MSM will be instructed to use lubricant with all anal sex acts. Coital log entries indicating incorrect use of lubricant will be excluded from clinical failure analyses (Aims 3 and 4). This includes use of non-study lubricant, use of lubricant inside the condom, and absence of lubricant use for anal sex.

### 6. TRIAL DESIGN

### 6.0 Study Arms

The study will have two arms: 252 eligible MSM and 252 eligible MSW. Within each study population, we will randomly assign the sequence in which study condoms (fitted, thin, and standard) are received.

12

[figure not shown]

Figure 2. Study arms and crossover condition combinations

#### 6.1 Randomization

Eligible and consented study participants who complete their fitted condom self-measurement will be randomized to one of six crossover condition orders that balance the allocation of conditions (Table 1). The randomization sequence lists will be developed as follows. Within each study stratum (MSM or MSW), an unblinded data coordinator will develop permuted block randomization sequences in our electronic database, Dacima (see section 12.0 for more detail). The block sizes will be randomly chosen (e.g., 6, 12). These randomization sequences will be stored in Dacima. Following successful completion of baseline study visit procedures and self-measurement for fitted condoms, the participant will be automatically randomized by being assigned the next available crossover condition in the sequence within that participant's stratum. Dacima will then indicate to study staff which crossover condition to distribute at the baseline visit (or to mail if sizing occurred at home after the baseline visit) and appropriate subsequent study visits.

1 able 1. Kallubilized Clossovel bluels									
	Crossover Condition								
Combination	1	2	3						
1	Fitted	Thin	Standard						
2	Fitted	Standard	Thin						
3	Thin	Fitted	Standard						
4	Thin	Standard	Fitted						
5	Standard	Fitted	Thin						
6	Standard	Thin	Fitted						

Table 1. Randomized crossover orders

### **6.2 Blinding Procedures**

In this closed label, double-blind trial, study condoms will be manufactured in plain foil packaging, with identifying two-digit random codes printed on each foil. Thin condoms will have a two-digit code, standard condoms will have a two-digit code, and each fitted condom size will have a random two-digit code to maintain blinding. Unblinded study staff will separate each condom type into different colored bags to allow for participants and study event staff to easily discriminate between the condom types. The randomization codes will be presented to study staff in a manner that supports blinding, using the color of the study condition to identify the condom to be distributed to a participant.

Blinding of study staff will be role-based. The study statistician and the principal investigator, who are responsible for analyses and reporting results to FDA, will be blinded until after the initial analysis of study results has been reported to FDA. Participants will also be blinded in order to minimize bias. The different condom types were matched to three different colors. These colors will be used to guide the process of condom distribution in the study. The colors, rather than the fitted, thin, and standard condom types, were entered into Dacima. Study staff who are not involved in the assessment of outcomes or analyses may be unblinded as needed to dispense the appropriate condoms to participants, but will be trained in how to interact with blinded participants without disclosing allocations or otherwise influencing participants.

We recognize an inherent limitation to the blinding scheme in that some participants may be able to detect their assigned condition. In particular, some participants may be able to identify fitted condoms due to potential size difference from standard condoms. Similarly, some participants may be able to detect a thin condom due to thickness difference from standard condoms. We will seek to mitigate this potential bias by recording the perceived study condom assigned, and assessing in secondary analyses whether participants who are able to detect their assigned study condition report differently on key outcomes than participants who are unaware of their study condition.

Based on previous trials, we expect possible adverse events (AE) to include symptomatic and asymptomatic STIs (particularly in area not covered by condom), acute HIV infection, discomfort or other issues related to the study condoms or lubricant, and pregnancy (for current partner of MSW) (described in Section 8.1.1).

If any adverse event occurs at a rate of 1.5 times greater than expected, the principal investigator will consider unblinding the study at the investigator level, in consultation with the study physician. Assuming that we will follow people on average for 10 weeks, we expect chlamydia and gonorrhea among MSW to occur among less than 0.5% of participants during the study period, based on 2013 surveillance data for men in Georgia. Based on estimates from a previous study in Atlanta we expect urethral chlamydia and gonorrhea among MSM to occur among less than 1% of participants and rectal chlamydia and gonorrhea among MSM to occur among less than 4% of participants during the study period.

Given that there is a 50-90% rate of acute symptoms among incident HIV infections and an 11% incident rate of HIV observed among young black MSM in Atlanta, we expect over the 6-10 week study period acute HIV infection among 1.3% of MSM participants. Because there are limited data available regarding incidence HIV rates among MSW in Atlanta, we estimate acute HIV infections to be one-fifth of that for MSM, or 0.25% of MSW participants.

Discomfort or other issues related to the study condoms or lubricant are expected to occur at a rate of 20% ([name], email communication, August 11, 2015). Pregnancy for current partners of MSW is expected to occur among less than 4% of partners during the study period. However, we expect 52% of MSW and their current partners will not be using condoms as the main form of birth control.

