#### 3. STUDY OVERVIEW

# 3.0 Study Design

This study is a randomized crossover trial of 252 HIV-negative MSM and 252 HIV-negative MSW. Every participant in the trial will receive a batch of five fitted condoms, a batch of five thin condoms, and a batch of five standard condoms over a series of study visits. We will randomize the order in which fitted, thin, and standard condoms will be distributed. Eventlevel data based on a home coital log will be collected regarding pleasure and total clinical failure (Aims 1, 3 and 4), and data regarding overall condom preference (Aim 2) will be collected at the final study visit. All participants will complete an informed consent form (ICF) (uploaded to eIRB). Eligibility assessment will include HIV testing and symptomatic STI and acute HIV screening. The order in which study condoms will be received will be determined by permuted block randomization. Participants will be provided access to a mobile-optimized, web-based home coital log diary that is 21 U.S. Code of Federal Regulations (CFR) Part 11 compliant, in which participants will document each instance of study condom use as soon as possible following any vaginal or anal sex acts. Log entries will include assessment of pleasure and clinical failure, as well as other pertinent information such as substance use, lubricant, and any potential events including errors during application. Participants will be enrolled over a period of approximately 6-12 months, depending on the speed of recruitment. Each participant will be followed for six to twelve weeks after enrollment, depending on their use of study condoms in each two-week period between study visits (Figure 1). Participants will return for a follow-up visit two weeks after baseline. Participants will be given up to four weeks to use each study condom set; after 4 weeks with a set of condoms, participants will be automatically crossed over into the next study condition. If all condoms are used within the first two weeks, participants will crossover to the next randomized study condoms at that point (Figure 1). If participants do not use all study condoms in the first two weeks after the have been dispensed, participants will be given a second 2-week period to use the batch of condoms. Throughout the duration of study participation, coital logs will be completed.

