### 7.1.3.4 Visit Adverse Event Screening

- Study staff will screen participants for symptoms of a STI or acute HIV infection using procedures from the baseline visit.
  - If the participant self-reports symptoms of any STI at follow-up, they will be referred to AID Atlanta for testing and treatment as needed. Participants symptomatic for STIs will receive their incentive for the visit and be study stopped. This will be recorded as an adverse event. See section 8.1.2 for more detail regarding adverse event reporting.
  - If the participant has had unprotected anal sex with a man OR has injected a substance not prescribed to him in the past 30 days AND self-reports symptoms of acute HIV infection, blood will be drawn for HIV viral load. Participants with acute HIV infection symptoms will receive their incentive and their study visit will end at this time.
    - Once study staff receive their laboratory results, if the participant has no detectable viral load, the participant will be allowed to return to complete their study visit. We will ship participants their next batch of condoms and schedule them for their next follow-up visit two weeks later.
    - o If the participant has a viral load that indicates acute HIV infection, they will be actively linked to HIV care. Results will be returned by study staff experienced in HIV care linkage (scripts uploaded to eIRB). The participant will be study stopped and study staff will record this as an adverse event.
- Study staff will ask participants if they have experienced any discomfort or issues related to the study condoms. If they indicate any, participants may be asked to have a picture taken of the reaction for the study clinician's assessment. Depending on the severity of issues, as determined by the clinical judgment of the study physician, they may be study stopped.
- For MSW participants, study staff will ask whether their current partner is pregnant.
  - If that participant indicates that their partner is pregnant and the expected date of conception is during the study or unknown, their partner will be referred to the Grady Family Planning Wellness Clinic and study staff will record this as an adverse event.

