#### 7.3 Measures

# 7.3.1 Visit Case Report Forms

Study staff will collect key data points using eCRFs at study visits. For the baseline visit, information to be collected on eCRF includes eligibility criteria, basic demographic information, and acute HIV and STI symptoms. For follow-up visits, eCRFs will include information regarding documentation of condition crossover, number of condoms distributed and returned, adverse events, and study stops.

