## 9.5 Study blinding

The study statistician and the principal investigator, who are responsible for analyses and reporting results to FDA, will be blinded until after the initial analysis of study results has been lodged with FDA. Participants will also be blinded in order to minimize bias. The different condom types were matched to three different colors. These colors will be used to guide the process of condom distribution in the study. The colors, rather than the fitted, thin, and standard condom types, were entered into Dacima. Study staff who are not involved in the assessment of outcomes or analyses may be unblinded as needed to dispense the appropriate condoms to participants, but will be trained in how to interact with blinded participants.

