ClinicalTrials.gov Study Title: Condom Performance in a Longitudinal Enhanced Assessment of User Experiences (C-PLEASURE)

ClinicalTrials.gov Identifier: NCT02753842

Statistical Analysis Document Date:

Submitted for publication to JMIR – September 13, 2018

Accepted for publication in JMIR – February 14, 2019

Submitted to ClinicalTrials.gov – July 20, 2020

Statistical Analysis

Statistical power and sample size

Using a sample size of $n=504$ randomized participants, assuming 80% retention to $n=403$, and $\alpha=0.05$ we estimated $> 99\%$ power to detect a statistically significant contrast for Aim 1 across a wide range of possible event-level pleasure scores. For Aim 2 at 80% and 90% power, assuming 80% retention, the minimum underlying values of fitted-condom preference $\pi_{2,1}$ that would be detectable as significantly higher than 0.5 ranged from 0.56 to 0.57. Given these calculations, we sought to have at least 404 participants complete the trial. Based on our previous studies in Atlanta, we anticipated 20% loss to follow-up from the 504 enrolled participants.

Data analysis

The planned primary analysis of Aims is described in Table 1.

Table 1. Outcome measures used to assess each study aim

	Aim	Outcome measure
1	To compare fitted condoms with standard condoms regarding levels of reported pleasure as determined by rating per condom use event	Pleasure-scale score (response item mean) for fitted condoms and standard condoms, following each coital event
2	To compare fitted condoms with standard condoms regarding preference as determined by dichotomous preference among the two conditions at the study conclusion	Binary preference of fitted versus standard condoms, at final study visit
3	To assess for fitted, thin, and standard condoms the total clinical failure rate of each type of	Binary occurrence of clinical failure for each type of condom, at each coital event

	condom for anal sex among MSM relative to a cut-point to be determined by the FDA	
4	To compare fitted condoms with standard condoms regarding total clinical failure for anal sex	Binary occurrence of clinical failure for fitted and standard condoms, at each coital event

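### The discomfort trigger has no stated unit and no split by condom type, and no adverse event comparison by condition is planned in the protocol or SAP, so a doubling on one condom would probably not reach it

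*Protocol*

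**What the plan says.** Protocol section 6.2 (Blinding Procedures) sets one safety trigger: "If any adverse event occurs at a rate of 1.5 times greater than expected, the principal investigator will consider unblinding the study" at investigator level, in consultation with the study physician. It then lists expected rates. Those for sexually transmitted infections are tied to participants and to the study period, and are given by arm; for example, "we expect chlamydia and gonorrhea among MSW to occur among less than 0.5% of participants during the study period". Acute HIV is also given by arm, and pregnancy for partners of MSW. The discomfort entry is different: "Discomfort or other issues related to the study condoms or lubricant are expected to occur at a rate of 20" per cent, sourced to an email, with no denominator and no period. It includes lubricant problems. No expected rate for any event is given by condom type.

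The design is a three-way crossover (section 3.0): "Every participant in the trial will receive a batch of five fitted condoms, a batch of five thin condoms, and a batch of five standard" ones.

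The data needed for a comparison by condition are largely collected already:
- Section 7.1.3.4, at each follow-up visit: "Study staff will ask participants if they have experienced any discomfort or issues related to the study condoms".
- Section 7.3.1, for follow-up visits: "eCRFs will include information regarding documentation of condition crossover, number of condoms distributed and returned, adverse events, and study stops".
- Section 9.5 (and 6.2): "The colors, rather than the fitted, thin, and standard condom types, were entered into Dacima".

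No adverse event summary or comparison by condition appears in protocol sections 8 and 9. The other areas of research interest in section 9.0 run to 15 items and include clinical failure by condom type, but none is an adverse event comparison. The SAP covers Aims 1 to 4 and has no safety analysis. Section 8.0 mentions a data and safety monitoring plan, which is not among the documents.

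**The concern.** In a crossover where everyone receives every product, a rate over the whole study mixes three exposures. Two condoms behaving as expected dilute an excess on the third, so a trigger set on the overall rate responds weakly to a problem with one product.

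Discomfort is where this matters most. It has by far the highest expected rate, and width, length and thickness, which are what distinguish the three condoms, could plausibly affect it. The trial seeks pleasure and preference claims for fitted condoms and an anal-sex indication for all three types (section 2). Those claims could be reported without any planned look at whether one type causes more discomfort.

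Discomfort can also pause or stop participation (section 4.4). A man stopped before the interim preference question (section 7.1.3.3) may contribute no preference, so stops that differ by condition also bear on Aim 2.

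The missing unit is a separate difficulty. Without it, two people applying the same trigger to the same data could reach different answers.

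**Working it through.** **Inputs.** Expected discomfort 20% and multiplier 1.5 (protocol 6.2); three conditions per man (3.0); 504 randomized and 403 retained (SAP, power section). The 20% has no stated derivation, so it cannot be reproduced. The retention figure can: 504 × 0.8 = 403.2.

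**Trigger.** 1.5 × 20% = 30%. Read literally, 1.5 times *greater* would be 2.5 × 20% = 50%. The 30% reading is used below because it is the more sensitive one.

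**Reading (a): 20% of men over the whole study, conditions independent (assumption).**
- Per-condition risk p = 1 − 0.8^(1/3) = 7.17%.
- One condom at k times p gives an overall rate of 1 − (1 − kp)(1 − p)².
- For k = 2: 1 − 0.8566 × 0.8618 = 26.2%, or 1.31 times expected, below 30%.
- Reaching 30% needs kp = 1 − 0.70/0.8618 = 18.8%, so k = 2.62.
- Chance that the observed overall rate still reaches 30% when k = 2 (binomial): 0.22 with 100 men, 0.046 with 403, 0.025 with 504.

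**Reading (b): 20% per man per condition, averaged over conditions.**
- For k = 2: (20 + 20 + 40)/3 = 26.7%, or 1.33 times expected, below 30%.
- Reaching 30% needs k = (90 − 40)/20 = 2.5.

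**Reading (c): 20% of men over the study, complete overlap.** The same men react to every condom, and the doubled one affects 40%. The overall rate is 40% and the trigger is met.

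**Between (a) and (c).** A latent-normal model with equal correlation between a man's three conditions, calibrated to 20% overall, gives the overall rate when one condom's risk doubles:

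| Latent correlation | Per-condition risk | Overall rate |
|---|---|---|
| 0 | 7.2% | 26.2% |
| 0.5 | 9.0% | 26.3% |
| 0.8 | 11.9% | 27.5% |
| 0.9 | 13.8% | 29.1% |
| 0.95 | 15.4% | 31.1% |

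The expected overall rate stays under 30% until the overlap is very strong.

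**If the trigger were 50%.** Under (a), k = (1 − 0.50/0.8618)/0.0717 = 5.9. Under (b), k = (150 − 40)/20 = 5.5, which would mean a 110% rate, so no excess on one condom could reach it.

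**The same 1.5 multiplier applied to each color code, one condom doubled.**

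| Reading | Threshold | True rate | Chance reached, n = 100 / 403 | Chance reached with no excess, n = 100 / 403 |
|---|---|---|---|---|
| (a) | 10.8% | 14.3% | 0.87 / 0.98 | 0.10 / 0.004 |
| (b) | 30% | 40% | 0.985 / >0.999 | 0.011 / about 10⁻⁶ |

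These are for one condition at one look. The last column rises with three conditions and repeated looks, most noticeably early on under (a). The comparison shows how much information the overall rate discards; it is not a proposed stopping rule.

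**The case against.** A reader might infer that adverse events are watched only for the pooled trial, never by condom type, and that a doubling would therefore go unnoticed. The documents do not support that.

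- **Pooling is inferred.** Section 6.2 does not say the discomfort rate is pooled. That is the natural reading because no rate is given by condom, and several other rates are given by arm.
- **A governing document is not shown.** The data and safety monitoring plan in section 8.0 is a natural home for tabulation rules. What can be said is that no comparison by condition appears in the protocol or SAP.
- **Individual cases are seen.** Men with discomfort are paused until a physician assesses severity (4.4); an independent physician is consulted on reactions (7.2.5); the principal investigator reviews adverse event reports (8.0) and decides on relatedness (8.1.2). None of this is a rate comparison, and the principal investigator is blinded to type, but the events are not invisible.
- **The exposure is limited.** Each man is due five condoms of a type, all are FDA-cleared (10.2), and latex formulation and lubricant are common to all types (section 1). Because the 20% includes lubricant problems, doubling the whole rate for one type may overstate a condom-specific effect.
- **Attribution is imperfect.** Batches are withheld until crossover (7.1.2.6), so a screening interval generally reflects one condition, but the discomfort question has no stated recall window.

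These points limit the claim without answering it. The missing unit, the lack of a split by condition and the absence of any safety analysis in the SAP remain.

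**Conclusion.** The concern holds in a limited form. The discomfort trigger rests on one 20% figure with no unit and no split by condom, and the documents available plan no adverse event comparison by condition. A doubling on one type would give an overall rate of about 26% to 27% under the two direct readings, against a trigger of 30%, and would probably not reach it. One condom would need about 2.5 to 2.6 times its expected rate before the overall figure was expected to do so. No planned analysis would then show which type was responsible.

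The size depends on two things that the documents do not settle: the unit of the 20%, and how far the same men react to every condom. With nearly complete overlap the trigger would be met, though the planned analyses would still not attribute the excess to a type. The primary efficacy and failure analyses are not invalidated. This is a cheap improvement to safety monitoring and reporting.

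**What to change.** 1. In section 6.2, state the unit of the 20% (per man over the study, per man per condition, or per use), and whether the trigger means 1.5 times expected or 1.5 times above it.
2. Have the unblinded data coordinator tabulate, by color code, men exposed and men with discomfort, a pause or a study stop. Send this to the study physician separately from the weekly team report in section 8.0, so that the principal investigator and statistician stay blinded.
3. Record on the adverse event eCRF the condition in use at onset, so that attribution does not rest on visit timing.
4. Add to the SAP an adverse event table by condom type, with within-person fitted-versus-standard and thin-versus-standard comparisons of any discomfort. Where visits are already complete, this item can still be done.

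The cost is one extra database report, one added eCRF field and one extra SAP table. The downside is a small risk that a marked difference between colors hints at a type, which is why the table should not reach the blinded analysts. Early tables will be noisy: under reading (a), with 100 men, a condition with no excess has about a 10% chance of exceeding 1.5 times its expected rate at a single look.
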